12.2 Sample Size/Accrual Rate

It is anticipated that this trial will accrue a mimimum of 3 patients and a maximum of *18 patients in the phase 1 portion of this protocol and 16 patients in the phase 2 portion of the trial. (*Due to four patients receiving 40mg/kg rather than three, 19 total patients will be studied in phase 1. Protocol deviation approved by IRB on 17 Oct 2013.)

Total accrual of a maximum of 34 patients in 48 months is expected.

Assuming that the estimated success rate of resection is 0.70, with a sample size of 34, we will have 80% power to detect a moderate kappa of 0.490 from the null hypothesis of zero intraclass kappa, using a large sample 0.050 level two-sided test.

Descriptive statistics will be presented as mean and standard deviation for continuous variables, as frequency and percentage for categorical variables. SAS 9.1 will be used to perform the statistical analyses, type I error (significance level) will be set as 0.05.

32

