4.1.1 Treatment Protocol

A maximum of thirty-three subjects with malignant brain tumors will participate in this trial. Each patient will have been evaluated and found to have a malignant brain tumor by history and recent imaging studies (MRI) and deemed a surgical candidate based on current neurosurgical standards of care. Consent will be obtained by the principal investigator or co-investigator. Three subjects will be enrolled in each of the five phase 1 dose levels seen below according to the rules seen in the table in section 4.2.1. After establishment of the safest effective dose, an additional 16 subjects will be enrolled at that dose level for the phase 2 study. The protocol is divided into two parts; the surgical procedure part and the post operative treatment part.

Dose-Escalation Schedule				
Dose Level	Dose of 5-ALA			
Level 1	10 mg/kg			
Level 2	20 mg/kg			
Level 3	30 mg/kg			
Level 4	40 mg/kg			
Level 5	50 mg/kg			

IRB NUMBER: 12-135

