4.2.1 Dose-Escalation Scheme

Dose escalation will proceed within each cohort according to the following scheme. Three subjects will be entered sequentially at each of the five dose levels (10, 20, 30, 40, and 50 mg/kg). This dose escalation scheme is more aggressive than standard accelerated dose escalation schemas published because we are already aware of safety data from Europe demonstrating no toxicity with oral doses of 50 mg/kg. An additional three subjects will be added to the recommended phase 2 dose level according to the following scheme. Three subjects are planned at each dose level in order to ensure that sufficient samples are available to determine fluorescent intensity differences between normal and malignant tissue at each dose level.

IRB NUMBER: 12-135

Each dose escalation will be approved by a Data Safety Monitoring Board determined by SCRIHS (see Section 11.5).

Dose Escalation and Modification Rule Table

# of Patients with DLT at a Given Dose Level	Escalation Decision Rule
0 out of 3	Enter 3 patients at the next dose level.
≥ 2 out of 3	Dose escalation will be stopped. This dose level will be declared the maximally administered dose (highest dose administered). Three (3) additional patients will be entered at the next lowest dose level if only 3 patients were treated previously at that dose.
1 out of 3	Enter at least 3 more patients at this dose level. - If 0 of these 3 patients experience DLT, proceed to the next dose level. - If 1 or more of this group suffer DLT, then dose escalation is stopped, and this dose is declared the maximally administered dose. Three (3) additional patients will be entered at the next lowest dose level if only 3 patients were treated previously at that dose.
<1 out of 6 at highest dose level below the maximally administered dose	This is generally the recommended phase 2 dose. At least 6 patients must be entered at the recommended phase 2 dose.

4.2.2 Phase 2 accrual of 16 additional subjects at the recommended phase 2 dose will commence once the phase 1 portion of this trial is completed. All correlative studies will be continued in the phase 2 portion of the study in order to define the differential fluorescence between normal and malignant brain tissue, enhancement of tumor resection, and survival impact of preoperative 5-ALA.

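### The stated maxima of 33 (4.1.1) and 34 (12.2) are below the 35 implied by 12.2's own footnote, and 18 is a planned phase 1 size rather than a maximum

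*Combined protocol and SAP*

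**What the plan says.** Enrolment is stated in several places in the combined protocol and SAP.

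- **Section 12.2, main text:** a "maximum of *18 patients in the phase 1 portion of this protocol and 16 patients in the phase 2 portion of the trial", followed by "Total accrual of a maximum of 34 patients in 48 months is expected".
- **Section 12.2, footnote to the 18:** because four patients rather than three received 40 mg/kg, "19 total patients will be studied in phase 1". The footnote records IRB approval of the deviation on 17 October 2013. The schema and section 11.5 carry the same footnote and also call 18 a maximum.
- **Section 4.1.1:** "A maximum of thirty-three subjects with malignant brain tumors will participate in this trial". The same paragraph builds the trial from its parts: "Three subjects will be enrolled in each of the five phase 1 dose levels", and then "After establishment of the safest effective dose, an additional 16 subjects will be enrolled at that dose level".
- **Section 4.2.1, text:** beyond the five cohorts of three, "An additional three subjects will be added to the recommended phase 2 dose level according to the following scheme".
- **Section 4.2.1, rule table:** after one DLT in three patients, "Enter at least 3 more patients at this dose level". If none of the added patients has a DLT, escalation continues. The table does not limit how many levels may be expanded in this way.

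The last row of that table describes the usual phase 2 dose as the level below the maximally administered dose, and requires at least six patients at the dose chosen. The table declares a maximally administered dose only when escalation is stopped.

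**The concern.** A stated maximum should be the largest number that following the protocol can produce. Neither total passes that test. The course described in 12.2's footnote gives more patients than 12.2 allows and more than 4.1.1 allows. The two sections also disagree with each other.

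The phase 1 figure has a separate problem. It is labelled a maximum in three places, yet the dose-escalation table can require more patients than that without any departure from the protocol.

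The IRB, the DSMC and the FDA look to the maximum when judging how many people will be exposed to an investigational agent. A figure that compliant conduct can exceed invites needless deviation reports, or pressure to cut short an expansion cohort that the safety rules call for.

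**Working it through.** **Inputs.** Five dose levels, three patients per level and three more at the recommended phase 2 dose (4.2.1); 16 patients in phase 2 (4.1.1, 12.2); 19 in phase 1 after the deviation (12.2 footnote); stated totals 33 (4.1.1) and 34 (12.2); expansion of at least three after one DLT in three (4.2.1 table).

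**Step 1: reproduce the plan's own total.**
- Phase 1: 5 × 3 + 3 = 18.
- Total: 18 + 16 = 34. This matches 12.2 before the deviation.

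**Step 2: carry the footnote through.**
- 19 + 16 = 35.
- 35 − 34 = 1 above the maximum in 12.2; 35 − 33 = 2 above the maximum in 4.1.1.

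**Step 3: try to recover the 33.**
- From the parts given in 4.1.1: 5 × 3 + 16 = 31.
- With the three extra patients from 4.2.1: 18 + 16 = 34.
- With the footnote: 35.
- None of these is 33, so 4.1.1 disagreed with 12.2 even before the deviation.

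**Step 4: test 18 against the 4.2.1 table.** Take cohorts of three and read an expansion as exactly three.
- One expansion suffices to pass 18. If 20 mg/kg is expanded and cleared, and 50 mg/kg is then taken to six as the recommended dose, phase 1 is 3 + 6 + 3 + 3 + 6 = 21.
- If every level has one DLT in the first three, and each of the first four clears its expansion, all five levels reach six: 5 × 6 = 30. With phase 2 the total is 30 + 16 = 46.
- The table says at least three, so 30 and 46 are ceilings only if each expansion is exactly three. They also assume cohorts of three; the fourth patient at 40 mg/kg falls outside the table.

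**Step 5: does the total matter for power?** Section 12.2 claims 80% power at N = 34 for kappa 0.490 against zero, two-sided 0.05. For a large-sample test of zero intraclass kappa the null variance is 1/N, so power = Φ(√N × 0.49 − 1.96).

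| N | √N × 0.49 | minus 1.96 | Power |
|---|---|---|---|
| 33 | 2.815 | 0.855 | 0.804 |
| 34 | 2.857 | 0.897 | 0.815 |
| 35 | 2.899 | 0.939 | 0.826 |

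The stated 80% is reproduced to within 2 percentage points at N = 34, and it holds at all three totals. The DLT stopping rules use counts within a dose level, so the overall total does not enter them.

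**The case against.** The best defence is that the gap between 34 and 35 is disclosed. The footnote appears wherever 18 is called a maximum, and it gives the cause, the new count and the IRB approval. The total of 34 was correct before the deviation, and 12.2 is phrased as a forecast. This stands: it is a total that was not updated, not a hidden excess. A reader might infer that the trial overran its approved enrolment, or that its true size cannot be known. The documents support neither, because the correction sits beside the 34 and the deviation was approved. The defence does not reach the 33, which nothing explains.

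A second defence is that the question about 18 has largely been overtaken. The footnote's 19 is 18 + 1, which fits 3 + 3 + 3 + 4 and then 3 + 3 at 50 mg/kg, with no DLT expansion below that dose. That allocation is an inference, but a reasonable one. A reader might go further and infer that phase 1 was likely to exceed 18. The documents give no DLT rate, so no probability can be attached. The point is only that the label is wrong under the protocol's own rules.

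A third tempting reading is that the phase 2 dose is undefined, or falls to 40 mg/kg, if 50 mg/kg is completed without a stop. That goes too far. The table row is qualified by the word generally, 4.1.1 asks for the safest effective dose, and 11.5 has the DSMC review side effects and fluorescence. Reading the row as pointing to 40 mg/kg applies a label for a declared stop when no stop was declared. What remains is a wording gap. Section 4.2.1 cites European data showing no toxicity at 50 mg/kg, so completion without a stop is the outcome the authors expect, and the row does not address it.

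**Conclusion.** The concern holds as an inconsistency in stated numbers, and it is minor. The maximum in 12.2 is 1 too low and the maximum in 4.1.1 is 2 too low against the 35 that 12.2's footnote implies. This needs no assumption beyond adding 19 and 16. The 18 is a planned phase 1 size without DLT expansions. The table permits up to 30 in phase 1 and 46 overall, assuming cohorts of three and expansions of exactly three.

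It should not be read as a power problem, since power stays between 0.80 and 0.83 across the three totals, or as a safety defect, since the stopping rules are untouched. The wording of the phase 2 dose row is a secondary clarification only.

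**What to change.** 1. In 4.1.1 and 12.2, replace 33 and 34 with a planned total of 35 (19 + 16).
2. In the schema, 11.5 and 12.2, describe 18 (now 19) as the planned phase 1 size without further DLT expansions, and stop calling it a maximum. Add that each expansion under 4.2.1 adds three patients, with a rule-based ceiling of 30 in phase 1 and 46 in total. Make clear that 35 is the plan and 46 the ceiling, so that two totals do not compete. If 30 and 46 are printed, the table should say exactly three where it now says at least three.
3. As a clarification, have the last row of the 4.2.1 table state which dose goes forward if 50 mg/kg is completed without a stop. The sponsor should name the dose, or name the safety and fluorescence criteria that decide it.

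The cost is amendment wording in five places. No patients are added for the course already described, and the power statement need not be recomputed. The one drawback is that the stated maximum becomes less favourable.

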APPENDIX A

Performance Status Criteria

ECOG Performance Status Scale		К	arnofsky Performance Scale
Grade	Descriptions	Percent	Description
	Normal activity. Fully active, able to carry on all pre-disease performance without restriction.		Normal, no complaints, no evidence of disease.
0			Able to carry on normal activity; minor signs or symptoms of disease.
1	Symptoms, but ambulatory. Restricted in physically strenuous activity, but ambulatory and able		Normal activity with effort; some signs or symptoms of disease.
to carry out work of a light or sedentary nature (e.g., light housework, office work).		70	Cares for self, unable to carry on normal activity or to do active work.
2	In bed <50% of the time. Ambulatory and capable of all self- care, but unable to carry out any work activities. Up and about more than 50% of waking hours.		Requires occasional assistance, but is able to care for most of his/her needs.
			Requires considerable assistance and frequent medical care.
3	In bed >50% of the time. Capable of only limited self-care, confined	40	Disabled, requires special care and assistance.
3	to bed or chair more than 50% of waking hours.		Severely disabled, hospitalization indicated. Death not imminent.
4	4 100% bedridden. Completely disabled. Cannot carry on any self-care. Totally confined to bed or chair.		Very sick, hospitalization indicated. Death not imminent.
4			Moribund, fatal processes progressing rapidly.
5	Dead.	0	Dead.

APPENDIX B

Ultraviolet-Illuminated Operating Room Microscope

Tumor Dye Project – Technical Aspects

5-aminolevulinic acid (5-ALA) – a naturally occurring non-fluorescing metabolic precursor, induces synthesis of protoporphyin IX (PpIX). PpIX fluoresces when exposed to the excitation light of blue-violet (wavelength 375-400nm.) It gives off a light with characteristic peaks 635 and 704nm. This is best viewed by filtering (440 long pass filter) out most other wavelengths except a small amount of excitation light.

The excitation light source is a 400 W short-arc Xe-lamp and a short pass filter (440nm.) integrated into a standard Leica surgical microscope. This filter can be switched on or off by the surgeon when needed. Light is delivered through a commercially available liquid light guide. The Leica OH series microscope is modified so that these filters can be switched on and off whenever the surgeon wishes to observe the fluorescence.

Two special filters for the 5-ALA fluorescence are used in a standard Leica OH microscope. The filters are a short pass (<440nm) filter which rotates in front of the microscope's standard 400-watt Xe light source. In addition, a special long pass (>440nm) barrier filter in the optical path allows clear viewing of the red fluorescence. Both filters are inserted and removed with one button on the microscope handle. With the push of that one button, the standard Leica OH microscope can then go back to being the neurosurgical and spine microscope it was designed for.

Using these modifications intraoperative detection of tumor fluorescence is possible without disturbing the routine of the surgical procedure. Switching between the two illumination modes does not require significant surgeon optical accommodation and does not interrupt the operation. All of these modifications are readily made to the standard neurosurgical microscope and requires no additional personnel in the operating room.

Appendix	С
Eligibility	Checklist

ppendix C ligibility Checklist	

Clinical/Radiological evidence of a primary malignant brain tumor	
Age ≥ 18 years old	
ECOG Performance Status ≤ 2	
Karnofsky ≥ 60%	
Leukocytes ≥ 3,000/mcL	
Absolute neutrophil count ≥ 1,500/mcL	
Total bilirubin within normal institutional limits	
AST (SGOT)/ALT(SGPT) ≤ 2.5 X institutional upper limit of normal	
Creatinine within normal institutional limits	
or Creatinine clearance ≥60mL/min/1.73 m ²	
Not pregnant	
Able to understand and sign informed consent	
Not currently treated with other investigational agents	
Not allergic to 5-ALA or similar drugs	
No personal or family history of porphyria	
No uncontrolled intercurrent illness including, but not limited to ongoing or	
active infection, symptomatic congestive heart failure, unstable angina	
pectoris, cardiac arrhythmia, or psychiatric illness/social situations that would	
limit compliance with study requirements	

	Date	Time	Initials	Result
Pre-op				
5-ALA Administration (dose)				
, , ,				
Intra-op				
Neurosurgeon [name] (circle one)				
Tumor Visualization with UV Illumination				
Photos Done?				
Pathologist				
White Light / Intensity by light meter				
Area of obvious tumor identified				
- Biopsy obtained?				
Biopsy code label				
- Fluorescence grade				
Area of normal brain in cavity identified				
-Biopsy obtained?				
Biopsy code label				
-Fluorescence grade				
Blue Light				
A				
Area of strong fluorescence identified				
- Biopsy obtained?				
Biopsy code label				
- Fluorescence grade				
Area of weak fluorescence identified				
- Biopsy obtained?				
Biopsy code label				
-Fluorescence grade				
Area of no fluorescence identified				
- Biopsy obtained?				
Biopsy code label				
- Fluorescence grade				

Appendix C	
Post-operative	Data

Post-op MRI	Date		
Evaluation Method (Circle one)	dsMRI	Manual	
Extent of Resection:	Gross total	Near Total	Incomplete
Liver Function Tests			
AST (SGOT)/ALT(SGPT)			
Bilirubin			

	Appendix C
Pathologist Re	
Surgical Patriol	logy Number
Code	Pathology Summary ☐ Solid tumor ☐ Infiltrating tumor/normal brain ☐ No tumor (edematous peritumoral normal brain) ☐ Other ☐ Solid tumor ☐ Infiltrating tumor/normal brain ☐ No tumor (edematous peritumoral normal brain)
	□ Other
	□ Solid tumor □ Infiltrating tumor/normal brain □ No tumor (edematous peritumoral normal brain) □ Other
	□ Solid tumor □ Infiltrating tumor/normal brain □ No tumor (edematous peritumoral normal brain) □ Other
	☐ Solid tumor ☐ Infiltrating tumor/normal brain ☐ No tumor (edematous peritumoral normal brain)

☐ Other_____ ☐ Solid tumor

☐ Other

☐ Infiltrating tumor/normal brain

☐ No tumor (edematous peritumoral normal brain)

Biops	y/Fluorescence
Corre	ations

Appendix C			

Biopsy Results ————————————————————————————————————					
Code/Type	Strongly Fluorescent	Weakly Fluorescent	No Fluorescence		
	☐ Solid tumor	☐ Solid tumor	☐ Solid tumor		
	☐ Infiltrating tumor/normal	□ Infiltrating	□ Infiltrating		
□ WL/T	brain	tumor/normal brain	tumor/normal brain		
□ WL/N	☐ No tumor (edematous	☐ No tumor (edematous	☐ No tumor (edematous		
□BL	peritumoral normal brain)	peritumoral normal	peritumoral normal brain)		
		brain)			
	☐ Solid tumor	☐ Solid tumor	☐ Solid tumor		
	☐ Infiltrating tumor/normal	□ Infiltrating	□ Infiltrating		
□ WL/T	brain	tumor/normal brain	tumor/normal brain		
□ WL/N	☐ No tumor (edematous	☐ No tumor (edematous	☐ No tumor (edematous		
□BL	peritumoral normal brain)	peritumoral normal	peritumoral normal brain)		
		brain)			
	☐ Solid tumor	☐ Solid tumor	☐ Solid tumor		
	☐ Infiltrating tumor/normal	□ Infiltrating	□ Infiltrating		
□ WL/T	brain	tumor/normal brain	tumor/normal brain		
□ WL/N	□ No tumor (edematous	☐ No tumor (edematous	□ No tumor (edematous		
□BL	peritumoral normal brain)	peritumoral normal	peritumoral normal brain)		
		brain)			
	☐ Solid tumor	☐ Solid tumor	☐ Solid tumor		
	☐ Infiltrating tumor/normal	□ Infiltrating	□ Infiltrating		
□ WL/T	brain	tumor/normal brain	tumor/normal brain		
□ WL/N	□ No tumor (edematous	☐ No tumor (edematous	□ No tumor (edematous		
□BL	peritumoral normal brain)	peritumoral normal	peritumoral normal brain)		
		brain)			
	☐ Solid tumor	☐ Solid tumor	☐ Solid tumor		
	☐ Infiltrating tumor/normal	☐ Infiltrating	□ Infiltrating		
□ WL/T	brain	tumor/normal brain	tumor/normal brain		
□ WL/N	□ No tumor (edematous	☐ No tumor (edematous	☐ No tumor (edematous		
□BL	peritumoral normal brain)	peritumoral normal	peritumoral normal brain)		
		brain)			
	☐ Solid tumor	☐ Solid tumor	☐ Solid tumor		
	☐ Infiltrating tumor/normal	☐ Infiltrating	☐ Infiltrating		
□ WL/T	brain	tumor/normal brain	tumor/normal brain		
□ WL/N	☐ No tumor (edematous	☐ No tumor (edematous	☐ No tumor (edematous		
□BL	peritumoral normal brain)	peritumoral normal	peritumoral normal brain)		
		brain)			

SCRIHS 10-035 5-ALA
Intra-Operative Data Sheet

Sample Code	Light	Area Biopsied	Fluorescence (0 to +++)
	□ White	☐ Obvious Tumor ☐ Obvious Not Tumor	
Time:	□ Blue	☐ Strongly Fluorescent ☐ Weakly Fluorescent ☐ No Fluorescence	
	☐ White	☐ Obvious Tumor ☐ Obvious Not Tumor	
Time:	□ Blue	☐ Strongly Fluorescent ☐ Weakly Fluorescent ☐ No Fluorescence	
	□ White	☐ Obvious Tumor ☐ Obvious Not Tumor	
Time:	□ Blue	☐ Strongly Fluorescent☐ Weakly Fluorescent☐ No Fluorescence	
	□ White	☐ Obvious Tumor☐ Obvious Not Tumor	
Time:	□ Blue	☐ Strongly Fluorescent ☐ Weakly Fluorescent ☐ No Fluorescence	
	□ White	☐ Obvious Tumor☐ Obvious Not Tumor	
Time:	□ Blue	☐ Strongly Fluorescent ☐ Weakly Fluorescent ☐ No Fluorescence	
	□ White	☐ Obvious Tumor ☐ Obvious Not Tumor	
Time:	□ Blue	☐ Strongly Fluorescent ☐ Weakly Fluorescent ☐ No Fluorescence	

Grade	Definition		
0	No fluorescence. No difference between any of the tissues	No	
	visualized.	fluorescence	
+	Low fluorescence. Red glow is barely distinguished from surrounding non-fluorescent tissue.	Weak	
++	Moderate fluorescence. Dull red glow of fluorescent tissue.	fluorescence	
+++	High fluorescence. Bright red glow of fluorescent tissue	Strong fluorescence	

Estimate	of extent of fluorescent tiss	sue
resected	(%):	

Estimate of extent of enhancing tumor resected (%):

C-6

